### 7.3 Punch Biopsies

Up to five (5) subjects will be consented to provide skin biopsies. Each subject will provide up to three (3) punch biopsies. 2 mm punch biopsies will be taken from the location on the face in an area of photoaging at discretion of investigating physician either pre-auricular or at temple hairline. If face location is unattainable the forearm (exposed to photoaging) may be used as an alternate biopsy location and will receive the combined laser treatment in addition to receiving a facial treatment. Pre- and post-treatment biopsies must be taken from the same general location for each patient.

[figure not shown]
Biopsies will be obtained using standard sterile technique after an intradermal local anesthesia, closed with suture (at the discretion of the Sub-Investigator/Study Physician), and treated with topical antibiotic and sterile dressing in routine fashion. Subjects' skin may be marked with a surgical marker to use as reference. Complete anesthesia of the biopsy site will be confirmed prior to the punch being inserted.

The biopsies will be immediately transferred into 10% formalin solution and stored at room temperature. Collected biopsy samples will be sent to Propath for biopsy sample analysis. IHC staining for Procollagen I, elastin, CD31, lymphocyte count, Masson's trichrome, GAG (Colloidal/Fe), and H&E, with images. 15 samples total will be collected (5 sets at baseline, day 14 and final visit).

The biopsy sample manifest will be sent to Propath and will contain the subject number, product information, total number of biopsies collected, and any other relevant information needed to identify the samples post-analysis.

#### 7.4 Visual Analog Scale (VAS)

The study subjects will be asked to complete an eleven point visual analog scale (VAS, 0-10) for the level of pain and discomfort associated with the study procedure to be completed by the subjects on the day of the procedure immediately after or within 60 minutes from the end of the procedure and recorded in the CRF treatment record. They may verbally respond with a numeric pain score.

Scoring will be reported by the provider on the treatment record.

### 7.5 Subject Satisfaction

Using a five (5) point Likert scale the study subjects will be asked to complete a satisfaction survey to rate their overall treatment results at the three-month follow-up visit.

Overall how would you rate your satisfaction with the	Very Dissatisfied	1
treatment results?	Dissatisfied	2
	Neither Satisfied nor Dissatisfied	3
	Satisfied	4
	Very Satisfied	5

### 7.6 Subject Modified Global Aesthetic Improvement Score

The Modified Global Aesthetic Improvement Scale (GAIS) is a subjective rating of improvement of treatment results compared to pre-treatment. The subjects will grade the overall improvement of the appearance of the treatment areas. The subject will compare their appearance at three months against a photograph taken at baseline.

SUBJECT MODIFIED GLOBAL AESTHETIC IMPROVEMENT SCALE			
Comparing baseline photograph to three-months photograph.	Rating		
	Very Much Improved		
How do you rate your overall appearance compared to before	Much Improved		
treatment?	Improved		
	No Change		
	Worse		
	Much Worse		
	Very Much Worse		

### 7.7 Independent Photographic Assessments

Two experienced, blinded photographic reviewers will compare 2D photographs via Canfield Scientific, Inc VISIA data access system:

- The reviewer will select between 2 sets of unmarked photos and determine which
  is baseline and one-month post treatment. Based on their selection of baseline to
  one-month post treatment the reviewer will rate improvement.
- 2. The reviewer will select between 2 sets of unmarked photos and determine which is baseline and three-months post treatment. Based on their selection of baseline to three-months post treatment they will rate improvement.

A Quartile Improvement Scale will be used to individually score each category: (a) fine wrinkles, (b) skin texture, (c) dyschromia/pigment, (d) skin radiance, (e) pore size and (f) overall appearance.

Blinded Investigator Quartile Improvement Score			
Rating	Percentage (%)	Score	
No Improvement	0%	0	
Minor/Mild Improvement	1%-25%	1	
Moderate Improvement	26%-50%	2	
Marked Improvement	51%-75%	3	
Very Significant Improvement	76%-100%	4	

If the incorrect order is selected that grouping will not be used to calculate improvement. The percentage of correct to incorrect will be calculated for both one-month and three-month assessments.

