#### 4.2.4 Exploratory Endpoints

- i. Subject Modified Global Aesthetic Improvement Scale (GAIS) comparing their own photos at 3 months post treatments compared to baseline photos.
- ii. Subject Satisfaction with procedure recorded at 3 months post treatments.
- iii. Five (5) patients will have 2-mm punch biopsies from area of photoaging comparing baseline to 14 days and 3 months post treatments (location on face at discretion of investigating physician: either pre-auricular or at temple hairline. If face location is unattainable, the forearm, exposed to photoaging may be used as an alternate biopsy location). Pre- and post-treatment biopsies must be taken from the same general location for each patient.
- iv. Blinded Investigator: analysis of unmarked 2D photo sets via Canfield clinical system. Reviewers will select the order of baseline and post treatment onemonth photos. Then based on their selection assess photos for percentage improvement in photoaging damage using the quartile improvement scale and score 0-4. Reported percent change in improvement of correct order sets.
- v. Blinded Investigator: analysis of unmarked 2D photo sets via Canfield clinical system. Reviewers will select the order of baseline and post treatment three-months photos. Then based on their selection assess photos for percentage

improvement in photoaging damage using the quartile improvement scale and score 0-4. Reported percent change in improvement of correct order sets.

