#### 6.5 Data Collection

Subject demographic information, procedural data, adverse events, treatment observations and study required assessments will be documented on the case report forms (CRFs). Study subjects will complete satisfaction and modified global aesthetic improvement scale evaluations at the 3-month follow up. The Investigators will assess post treatment skin effects immediately post treatment, at follow up visits (prolonged post treatment) and quartile improvement scores at one (1) month and three (3) months in comparison to baseline photography. Blinded Investigators will provide analysis of unmarked 2D photo sets via Canfield clinical system. Reviewers will select the order of baseline and post treatment at one (1) month and three (3) months. Then based on their selection assess photos for

percentage improvement in photoaging damage using the quartile improvement scale and score 0-4.

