#### Visit 1 (Day 0-30)

Screening

A prospective subject is to be examined to determine if they qualify for entry into the study. This initial examination will include:

- Obtain written Informed Consent and photographic release
- Review Inclusion/Exclusion Criteria
- Record Medical History/Meds/Vital Signs
- Urine Pregnancy Test (if applicable): only one is necessary prior to start of treatments.
- Dispense CeraVe® Products
- Skin types IV-VI: Begin Hydroquinone 8% QHS at discretion of treating physician 2-3 weeks prior to first treatment. Hold while skin is healing, then restart QHS or as directed.
- Investigator Assessments: Glogau Photodamage, Fitzpatrick Skin Type and Wrinkle & Elastosis Scale
- Biopsy #1 of five patients (baseline)

Note: Screening and Baseline visits may occur on the same day for non biopsy patients.

#### Visit 2

Baseline/Treatment #1 (Screening/Baseline may be on same day)

This treatment visit will include:

- Photographs prior to treatment: wait at least 15 min indoors, 2D standard photography captured via Canfield VISIA CA.
- Urine Pregnancy Test (if applicable): only one is necessary prior to start of treatments.
- · Laser treatment to the face
- VAS Scale
- Post Treatment Skin effects (provider)
- Review for Adverse Events (provider)
- Subject Diary post treatment (7 days) given to patient.

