10.2.3 Minimization of Bias and Potential Confounding Factors
Blinded investigator photo evaluation is intended to minimize bias.

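### Both blinded photo pairs contain the same baseline set, so a reviewer who recognises the repeat can order at least the second pair without judging photoaging

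*Combined protocol and SAP*

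**What the plan says.** Section 7.7 sets up the reading: "Two experienced, blinded photographic reviewers will compare 2D photographs via Canfield Scientific, Inc VISIA data access system". Two numbered tasks follow. The first is to tell baseline from 1 month. The second is the same for the later visit: "The reviewer will select between 2 sets of unmarked photos and determine which is baseline and three-months post treatment". After each choice the reviewer rates improvement from 0 to 4 in six categories, on the basis of the order chosen. Section 6.5 describes one group of readers doing both tasks: "Reviewers will select the order of baseline and post treatment at one (1) month and three (3) months". The synopsis and section 4.2.4 (items iv and v) agree, and none of these places divides the tasks between reviewers.

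The ordering result is used twice in 7.7. It decides which sets are scored: "If the incorrect order is selected that grouping will not be used to calculate improvement". It is also an output in its own right: "The percentage of correct to incorrect will be calculated for both one-month and three-month assessments".

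The baseline photographs are taken at Visit 2, before the first laser session: "Photographs prior to treatment: wait at least 15 min indoors, 2D standard photography captured via Canfield VISIA CA". The schedule in 6.8 shows no 2D photography at Visit 1, so each subject has one baseline set.

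Section 10.2.3 on bias is a single sentence: "Blinded investigator photo evaluation is intended to minimize bias".

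**The concern.** Taking the labels off the photographs hides the visit only if nothing else gives it away. Here the pairing does. If a reviewer sees two pairs of one subject and one set of images occurs in both, that set must be the baseline. Recognising a repeated image is a different task from judging photoaging, and it can succeed when the laser has done nothing.

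The primary and secondary endpoints are scored by the treating investigator, who knows the order of the photographs, and there is no control group. The blinded reading is the only counterweight that the protocol names. Its 0 to 4 scale has no category for worsening, so the improvement score cannot fall below its null value of 0. The percentage of correct orders is different: if nothing has changed and there is no other cue, it should be about 50%. The shared baseline can move that benchmark.

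**Working it through.** **Step 1: structure of the pairs.** Inputs: the two tasks in 7.7 and the single baseline set at Visit 2 (6.8). For each subject the pairs are {baseline, 1 month} and {baseline, 3 months}. Their only common element is the baseline. This holds for every subject whose two pairs go to the same reviewer.

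**Step 2: what protects the order.** I looked in 6.5, 6.5.1, 7.1, 7.7 and 10.2.3 for six safeguards: splitting the pairs between reviewers, separate sessions, shuffling across subjects, randomised position, decoy pairs, and locking an answer before the next pair opens. None is stated. Section 6.5.1 refers to a separate vendor manual, but describes it as covering the photography procedures and does not mention how images are shown to readers.

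**Step 3: which orders are exposed.** If 1-month answers are locked before 3-month pairs appear, only the 3-month order is exposed. If both pairs are open together, or answers can be changed, both orders are exposed.

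**Step 4: size with no treatment effect.** Let r be the share of subjects in whom the reviewer recognises the repeated set. This is an assumption; the documents give no value. A recognised subject is ordered correctly and the rest are guesses:

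P(correct) = r + (1 − r) × 0.5 = 0.5 + 0.5r

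Wrongly ordered sets are dropped, so the expected number kept per reviewer is n × (0.5 + 0.5r). The protocol enrols up to 30 subjects and bases its power statement on 25.

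| r (assumed) | Expected correct | Kept, n = 30 | Kept, n = 25 |
|---|---|---|---|
| 0 | 50% | 15 | 12.5 |
| 0.1 | 55% | 16.5 | 13.75 |
| 0.2 | 60% | 18 | 15 |
| 0.5 | 75% | 22.5 | 18.75 |
| 1 | 100% | 30 | 25 |

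**Step 5: size with a treatment effect.** If a reviewer orders a share c correctly by real judgement, the observed share becomes r + (1 − r)c. The inflation is r(1 − c). For c of 0.5 or more it is largest at c = 0.5, so the cue distorts most when the treatment does least.

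**Step 6: illustration only.** The SAP table does not test the percentage correct. As a yardstick for a result that would look convincing, 21 of 30 correct has an exact two-sided binomial p of 0.043 against 50%. With no treatment effect, the chance of at least 21 of 30 is 0.021 at r = 0, 0.069 at r = 0.1, 0.176 at r = 0.2 and 0.803 at r = 0.5.

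**The plan's own figures.** The plan states no figure for the ordering task. Its only design figure, more than 95% power with 25 subjects, concerns the investigator's score and has no bearing here.

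**The case against.** The strongest reply is that the plan is silent rather than wrong. It never says in so many words that each reviewer reads both pairs of every subject, and reading order, spacing and locking are simply not specified. The imaging vendor's system might shuffle or lock the readings. That stands as a limit on certainty. It does not supply a safeguard, and if one is intended, 7.7 is where it belongs.

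Recognition may also be less frequent than it first seems. Every set of a subject shows the same face. Section 7.1 standardises hair and removes makeup and jewelry, and views and lighting are fixed. What remains is expression and transient marks, across up to 30 subjects. On the other side, the repeated set consists of the very same images in three views. The documents do not settle the rate.

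A reader might infer that the blinded scores become worthless because reviewers rate improvement knowing which set is post-treatment. The documents do not support this. Under 7.7 every retained score already comes from a reviewer who had chosen the correct order. The shared baseline changes how the order may be reached and how many sets are kept. Its effect on the mean improvement score, the quantity the SAP does test for these readings, cannot be derived from the documents.

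A reader might also take the probabilities in Step 6 as error rates of the trial. They are not, because no planned test uses the percentage correct.

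**Conclusion.** The weakness is real and lies in how the pairs are built. It rests on the natural reading that each reviewer sees both pairs of a subject, and on the absence of any stated safeguard. The cue is available for every such subject, but it matters only where the repeated set is recognised. It would be too strong to say that the order is known in all subjects, or that the 1-month order is exposed in every case.

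The effect is a possible rise in the reported percentage of correct orders above its 50% no-effect value, to 0.5 + 0.5r, together with more sets kept for scoring. At r = 0.2, for example, that is 60% instead of 50%, and 18 sets kept instead of 15 among 30 subjects. The true r is unknown.

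The blinded readings are exploratory. A reader might infer that the effectiveness conclusion is compromised, but the primary and secondary endpoints are the treating investigator's scores and safety is assessed separately, so none of them is touched. What is weakened is the one check on bias that the protocol offers. That makes the change worth making before any images are read.

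**What to change.** In 7.7, with matching wording in the synopsis, 4.2.4 and 6.5:

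- Add a third pair per subject, 1 month versus 3 months, from photographs already scheduled. Each set then appears exactly twice, so repetition no longer identifies the baseline.
- Show all pairs in one list shuffled across subjects, with left/right position randomised and each answer locked on entry.
- Ask reviewers to pick the earlier of the two sets, and do not tell them which visits are shown.
- Exclude the decoy pair from the endpoint and from the percentage correct.

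Cost: each reviewer reads up to 3 × 30 = 90 pairs instead of 2 × 30 = 60, which is up to 30 more. Each decoy should be scored in all six categories so that it looks like the others. The ordering task is also reworded, from identifying the baseline to identifying the earlier set. No new visit, photograph or reviewer is needed.

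Alternative: split the pairs so that no reviewer sees a subject's baseline twice. One reviewer reads 1-month pairs for odd subject IDs and 3-month pairs for even IDs, and the other does the reverse. Readings fall to 30 per reviewer, but this is not free. Each pair gets one reading instead of two, and a subject's 1-month and 3-month scores come from different reviewers, so differences in leniency mix with time within a subject.

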#### **Exploratory Endpoints**

Subject Modified Global Aesthetic Improvement Scale (GAIS) comparing their overall appearance in photos at 3 months post treatments with baseline photos.

Subject Satisfaction with procedure recorded at 3 months post treatments.

Five (5) patients will have 3 punch biopsies from an area of photoaging comparing baseline to 14 days and 3 months post treatments (location on the face at discretion of investigating physician either pre-auricular or at temple hairline. If face location unattainable the forearm exposed to photoaging may be used as an alternate biopsy location).

Blinded Investigator: analysis of unmarked 2D photo sets via Canfield clinical system. Reviewers will select the order of baseline and post treatment onemonth photos. Then based on their selection assess photos for percentage improvement in photoaging damage using the quartile improvement scale and score 0-4. Reported percent change in improvement of correct order sets.

Blinded Investigator: analysis of unmarked 2D photo sets via Canfield clinical system. Reviewers will select the order of baseline and post treatment threemonths photos. Then based on their selection assess photos for percentage improvement in photoaging damage using the quartile improvement scale and score 0-4. Reported percent change in improvement of correct order sets.

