#### 7.2 Investigator Evaluations Quartile Improvement Score

Treating Investigators will compare:

- 1. Baseline photographs to one-month post treatment.
- 2. Baseline photographs to three-months post treatment.

A Quartile Improvement Scale will be used to individually score each category: (a) fine wrinkles, (b) skin texture, (c) dyschromia/pigment, (d) skin radiance, (e) pore size and (f) overall appearance.

Investigator Quartile Improvement Score				
Rating	Percentage (%)	Score		
No Improvement	0%	0		
Minor/Mild Improvement	1%-25%	1		
Moderate Improvement	26%-50%	2		
Marked Improvement	51%-75%	3		
Very Significant Improvement	76%-100%	4		

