#### 10.2.2 Additional Analysis

Additional analysis will be provided as following:

For IQIS (0-4), the mean score will be compared to a constant value of 0 to test the null hypothesis that there is no improvement after the product use, using the method described in the SAP table.

For GAIS and subject satisfaction data, a binomial (sign) test will be performed to test if the proportion of the combined designated favorable responses (Very Much Improved, Much Improved, and Improved for GAIS; Very Satisfied and Satisfied for subject satisfaction) is equal to the combined designated unfavorable responses.

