#### **Statistical Analysis Plan Table**

Evaluation	Change from baseline	Notes/Interpretation
Investigator	The mean score (0-4) will	Significantly greater than 0
Quartile	be compared to the	indicates improvement.
Improvement	constant 0, using Wilcoxon	
Score	signed rank test	
SAEs	NA	Zero or low number of SAEs is
		favorable
Tolerability	NA	Lower score indicates better
parameters		tolerability
VAS	NA	Lower score indicates better
		tolerability
Biopsy parameters	NA	Descriptive statistics only
Individual	NA	A binomial test (sign test) P value
response data		will be provided. A higher
(GAIS and		percentage of combined favorable
satisfaction)		responses with a significant P
		value indicates positive subject
		perceptions of the test material.
Blinded	The mean score (0-4) will	Significantly greater than 0 indicates
Investigators	be compared to the	improvement.
	constant 0, using Wilcoxson	
	signed rank test	

All statistical tests will be 2-sided at significance level alpha=0.05 unless specified otherwise. *P* values will be reported to 3 decimal places (0.000).

No multiple testing corrections will be considered in the study. Statistical analyses are performed using SAS software version 9.4 (SAS Statistical Institute). The statistical results will be sent to the Sponsor along with raw data in a Microsoft Excel document at completion of the study.

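### The blinded photo reading tests only correctly ordered pairs, on a 0-4 score, against 0, so the test can report improvement when readers are guessing the order; the order choice that could check this is not tested.

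*Combined protocol and SAP*

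**What the plan says.** Section 7.7 has two blinded readers who see unmarked photo sets, decide which is baseline, and then score six categories from 0 to 4. For the later time point: "Based on their selection of baseline to three-months post treatment they will rate improvement". Pairs put in the wrong order leave the improvement calculation: "If the incorrect order is selected that grouping will not be used to calculate improvement". The exploratory endpoints in the synopsis and in section 4.2.4 say the same: "Reported percent change in improvement of correct order sets".

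The order results are summarised: "The percentage of correct to incorrect will be calculated for both one-month and three-month assessments". No null value, test or threshold is attached to that percentage.

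In the Statistical Analysis Plan Table, the Blinded Investigators row compares the mean 0-4 score with the "constant 0, using Wilcoxson" signed rank test, and significance above 0 is to be read as improvement. That row does not repeat the exclusion; that it applies follows from section 7.7 and the endpoint wording. The treating investigators' score uses the same 0-4 scale (section 7.2: "A Quartile Improvement Scale will be used to individually score each category") and the same comparison (section 10.2.2: "For IQIS (0-4), the mean score will be compared to a constant value of 0 to test the null hypothesis"). Tests are two-sided at 0.05, and "No multiple testing corrections will be considered in the study".

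**The concern.** The scale has no value for worsening. In this reading, the only way evidence against the treatment can appear is a wrong order choice: a reader who takes the baseline set for the post-treatment set and scores a difference is saying that the baseline set looks better. Those pairs are left out, and what remains is tested for being above 0. The test can therefore move in one direction only, and it can be significant when readers cannot tell before from after.

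The study has no control group, the primary score comes from the treating investigators, and blinded photo evaluation is the one measure that section 10.2.3 names against bias. A p-value that can call guessing an improvement weakens that safeguard.

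**Working it through.** **Inputs from the documents.** Score range 0-4, two readers, six categories, two time points, and exclusion of wrong-order pairs (7.7). Signed rank test against 0, two-sided 0.05 (SAP table). N=25 is the size used for power and N=30 the maximum enrolment (10.1).

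**The plan's own figure.** Section 10.1 states more than 95% power at 25 subjects, for the primary endpoint. The mean and variance behind it are not given, so it cannot be recomputed, and nothing below depends on it. No power or error rate is stated for the blinded reading.

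**Assumptions.** One reader and one category; the exact version of the test; and q, the share of pairs scored 1 or more, which the documents do not give and which is shown as a range.

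**Step 1: when the test rejects.** With k non-zero kept scores, all positive, the exact two-sided p is 2 × (1/2)^k. For k=5 it is 0.0625; for k=6 it is 0.03125. Six non-zero scores suffice, whatever their values and however many orders were wrong.

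**Step 2: rejection rate under guessing.** A pair is kept with probability 0.5 and scored above 0 with probability q, so the rate is P(Bin(N, 0.5q) ≥ 6).

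| q | N=25 | N=30 |
|---|---|---|
| 0.1 | 0.1% | 0.3% |
| 0.2 | 3% | 7% |
| 0.3 | 16% | 29% |
| 0.5 | 62% | 80% |

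The rate equals 5% at q=0.220 (N=25) and q=0.182 (N=30).

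**Step 3: where the rate comes from.** If all pairs were kept without a sign, the rate would be P(Bin(N, q) ≥ 6): 38%/57% at q=0.2 and 81%/92% at q=0.3 (N=25/30). Those exceed the rates in step 2, so the inflation comes from the floor at 0, not from the act of dropping pairs.

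**Step 4: an illustration.** Take 30 subjects, every pair scored 1, and 15 orders right. The plan has k=15, so p = 2/2^15 = 0.00006. Giving wrong-order pairs a minus sign yields 15 positive and 15 negative scores of equal size, so p=1.0. This takes q=1 and is an extreme case.

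**Step 5: the mean.** Let c be the correct-order proportion, and assume kept and dropped pairs have the same mean m. The signed mean over all pairs is cm − (1−c)m = (2c−1)m: 0.4m at c=0.7, 0.8m at c=0.9, and m at c=1, where nothing is overstated.

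**Step 6: testing order against 50%.** The exact two-sided binomial test needs 18/25 (p=0.043; 17/25 gives 0.108) or 21/30 (p=0.043; 20/30 gives 0.099). Power per reader at N=25/30 is 51%/59% at 70% correct order and 89%/94% at 80%. If both readers must succeed and are independent (assumption), power is the square: 0.512² = 26% and 0.589² = 35% at 70%; 0.891² = 79% and 0.939² = 88% at 80%. Under guessing, the chance that both are significant in the favourable direction is at most about 0.043/2 = 2.2%, reached if the readers always agree.

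**Step 7: why a signed test is not the main remedy.** It holds about 5% when order is guessed. But one order choice signs every category. Simulating a category that has not changed (q=0.3, 90% correct order, scoring independent of order, non-zero scores 1/2/3/4 with assumed probabilities 0.60/0.25/0.10/0.05), the signed test rejects in 49%/61% of trials for one reader and about 85%/92% for the average of two independent readers (N=25/30). Overall appearance is not exempt if order is recognised from another category or cue.

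**The case against.** The strongest reply is that the order result is not hidden. Section 7.7 requires the correct-order percentage at both time points, and the endpoint is labelled as coming from correct-order sets, so a figure near 50% would be visible. This stands: a reader might infer that the plan throws direction away altogether, and the documents do not support that. Direction is left out of the score and its test, not out of the report. But a visible percentage without a null value or test corrects neither the p-value nor the mean beside it.

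A reader might also infer that dropping wrong-order pairs is what inflates the error rate. Step 3 shows otherwise. The floor is shared with the investigator score; what is particular here is that an order choice is collected that could correct it, and the test does not use it.

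Third, the size depends on q, and at low q the rate is below 5%. That also stands: the mechanism is certain, the magnitude is not.

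Finally, the reading is exploratory, and neither the sample size nor any stated success rule rests on it. It would be wrong to infer that the primary conclusion is compromised by this point.

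**Conclusion.** The concern holds in this limited form. The planned test of kept blinded scores cannot give a negative result, and six non-zero scores are read as improvement even if order is guessed. For one reader and one category the rate under guessing is 3%/7% at q=0.2, 16%/29% at q=0.3 and 62%/80% at q=0.5 (N=25/30), with q assumed. These are not the plan's overall error rates: no rule combines two readers, six categories and two time points, and there is no multiplicity correction. When some orders are wrong, the mean of kept pairs can also overstate the effect. The damage is to the value of the blinded reading as a bias control. It should be fixed before the readings are analysed.

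**What to change.** - In the SAP table, remove the signed rank test of kept blinded scores against 0.
- In section 7.7 and the SAP table, test each reader's correct-order proportion against 50% with an exact two-sided binomial test over all pairs. Name the 3-month reading as the main one, and require both readers to be significant in the favourable direction before claiming blinded improvement. Treat 1 month as supportive.
- Report all six category scores on correct-order sets descriptively, always beside the correct-order percentage.
- Retain the scores of wrong-order pairs. A signed overall-appearance mean over all pairs may be shown descriptively. A signed test, if kept, is supportive only, for the reason in step 7.

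No new readings are needed. The costs are a protocol amendment with IRB review (section 13.2), no p-values for category scores, and limited power when readers are only moderately accurate, lower still when both must succeed (step 6). The order test shows that readers can tell after from before, not by how much or through which feature; the descriptive scores have to be read with that in mind.
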